		Day 1	Day 2	Day 8	Day 29	Day 57	Day 85	Day 113	Day 169
				±1 day	±2 days	±3 days	±3 days	±3 days	±3 days
Lymphocyte Subsets (CD3-, CD4-, CD8-, CD20-, CD16-, CD56-positive) (central laboratory)	X	X ^c			X ^c	X ^c	X	X	
Randomization and Study Drug Administration									
Randomization		X							
Study Drug Administration		X			X	X			
Pharmacokinetics									
Plasma DS-7011a (central laboratory) ^d		X	X	X	X	X	X	X	
Pharmacodynamic and Other Biomarkers									
ESR and CRP (local laboratory)	X	X ^c			X ^c	X ^c	X	X	
Complement Factors (C3 and C4) (local laboratory at Screening and central laboratory thereafter)	X	X ^c			X ^c	X ^c	X	X	
SLE-related Autoantibodies (anti-nuclear, anti-dsDNA, anti-Sm, anti-RNP) (local laboratory at Screening and central laboratory thereafter)	X	X ^c			X ^c	X ^c	X	X	
TLR7 and IFN-Type I GS		X ^c	X	X	X ^c	X ^c	X	X	
Cytokines (central laboratory)		X ^c			X ^c	X ^c	X	X	
Skin Tape Harvesting for mRNA (central laboratory)		X					X	X	
Immunogenicity									
Anti-drug Antibodies (central laboratory)		X ^c			X ^c	X ^c	X	X	X ^e
Pharmacogenetics									
Blood sample for genotyping (central laboratory)		X ^c							

	Screening Period	Treatment Period						Follow-up Period ^a	
								EOT Visit	EOS Visit
Study Assessments and Tests	Within 4 weeks (28 days) prior to randomization	Week 0	Week 0	Week 1	Week 4	Week 8	Week 12	Week 16	Week 24
		Day 1	Day 2	Day 8	Day 29	Day 57	Day 85	Day 113	Day 169
				±1 day	±2 days	±3 days	±3 days	±3 days	±3 days
Patient Reported Outcome Questionnaires									
Quality of life questionnaires (Skindex-29+3 and SF-36)		X			X	X	X	X	
FACIT-Fatigue		X			X	X	X	X	
Itch NRS		X			X	X	X	X	
Patient's Global Impression of Change		X			X	X	X	X	

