3.1. Rationale for Selection of Primary Endpoints and Key Secondary and Exploratory Endpoints

The main scope of this Phase 1b/2 study is to explore DS-7011a safety and tolerability as primary objectives, to explore efficacy, PK, and immunogenicity properties as secondary objectives, and to explore PD properties as exploratory objectives. The rationale for the selection of IgM, IgG, and IgA values, vaccine (diphtheria, tetanus, and pneumococcus) titers, and lymphocyte subset (CD3-, CD4-, CD8-, CD20-, CD16-, and CD56-positive) values should allow an initial insight into DS-7011a immunosuppressive potential. Regarding clinical efficacy endpoints, in addition to overall SLE parameters, the selection of parameters such as the Cutaneous Lupus Area and Severity Index Activity (CLASI-A), which are descriptive of CLE, should favor an initial detection of potential for beneficial clinical activity, given the expectation that TLR7 plays a particularly prominent role in the development of this component of the SLE disease. Regarding clinical laboratory efficacy and PD endpoints, the selection of biomarkers reflects their mechanistic proximity to TLR7 activation (TLR7 GS expression), TLR7 role in SLE pathogenesis (cytokines and autoantibody concentrations), and inflammatory effects that cytokines and autoantibodies have (complement factors and MxA and inflammatory cell marker mRNA). Anti-Sm and anti-RNP autoantibodies will be assessed with particular interest, since their production may especially depend on TLR7 and therefore be blocked by DS-7011a.

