5.1. Inclusion Criteria

Subjects eligible for inclusion in this study have to meet all inclusion criteria for this study:

1. Male and female subjects must be of 18 years or more with definite SLE for at least 6 months prior to Screening, defined according to the 2019 European League Against Rheumatism (EULAR)/ American College of Rheumatology (ACR) classification criteria for SLE³, including documented history of positivity for antinuclear antibody (titer $\geq 1:80$).
2. Body mass index (BMI) ≥ 18 kg/m².
3. Presence of active CLE (acute, subacute, and chronic cutaneous lupus) with active skin involvement and a CLASI-A score of 4 or higher at the time of Screening and randomization, as recognized by 2 adjudicators, ie, the investigator in the periphery at the site and a centrally located arbiter contracted ad hoc (in case of disagreement between these 2 adjudicators, a third adjudicator, also centrally located and contracted ad hoc, will solve the disagreement and provide a final decision), despite adequate use of conventional therapies (either topical corticosteroids or antimalarial agents used for at least 12 weeks prior to Screening) or because of the requirement to discontinue these therapies due to side effects or poor tolerability.
4. Subjects must be willing to have skin tape harvests collected from the affected skin area (skin tape stripping done on the target lesion).
5. If the subject is a female of childbearing potential, she must have a negative serum pregnancy test at Screening and a negative urine pregnancy test at randomization, and she must be willing to use one method of highly effective birth control, as detailed in Section 10.2, and one barrier method, such as condom, diaphragm, or cervical cap with spermicide, upon enrollment, during the Treatment Period, and for 3 months following the last dose of study drug. A female is considered of childbearing potential following menarche and until reaching postmenopausal state, which is defined as no menstrual periods for a minimum of 12 months (a follicle-stimulating hormone [FSH] test may be conducted to confirm postmenopausal state according to investigator's discretion), unless made permanently sterile by surgery (undergone a hysterectomy, bilateral salpingectomy, or bilateral oophorectomy at least 1 month before the first dose).

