9.2. Sample Size Determination

The study will enroll up to 24 subjects with SLE in 2 parallel arms randomized to receive 2:1 DS-7011a or placebo. Tentatively, 9 of these 24 subjects will be of African descent. Also, tentatively, 9 of these 24 subjects will be positive for anti-Sm and/or anti-RNP autoantibodies.

The sample size selected is not based on statistical power considerations. The number of subjects in each arm is considered sufficient to achieve the objectives of this study. Initial evidence of DS-7011a efficacy will be inferred by the impact DS-7011a shows on clinical endpoints, mainly CLASI-A, and several mechanistic endpoints. This impact will be evinced by comparing endpoint values between DS-7011a-treated and placebo-treated subjects and between pretreatment (baseline) and post-treatment time points. Concomitant and consistent impact on multiple endpoints will be initial evidence of efficacy, especially if this impact is of large extent. DS-7011a extent of impact will be compared to that reported for antibodies approved (belimumab and anifrolumab) or in late phase of development (BIIB059) for the treatment of SLE². The result of this comparison will inform a DS-7011a “go/no-go” decision to further development.

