9.4.4. Modified Intent-to-treat Analysis Set

The Modified Intent-to-Treat (mITT) Analysis Set will consist of all randomized subjects who received at least one infusion of study drug.

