9.5.1. Efficacy Analysis

No primary efficacy measures or analysis are planned for this study; all efficacy measures will be secondary analyses.

All secondary efficacy analyses will be based on the mITT Analysis Set. The efficacy endpoints (CLASI-A, CLA-IGA, SLEDAI-2K, PGA-SLE, CGI-C, and PROs) will be summarized by treatment group using descriptive statistics. Comparison between treatment groups for the change from baseline to each visit in CLASI-A, CLA-IGA, SLEDAI-2K, PGA-SLE, CGI-C, and PROs, and laboratory parameters, such as autoantibodies (including antinuclear, anti-dsDNA, anti-Sm, and anti-RNP antibodies), complement factors (C3, C4), ESR, and CRP, will be summarized.

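### Change in anti-Sm and anti-RNP is summarised over all mITT subjects although only about 9 of 24 are planned to be positive for either, which can mask a real fall in the positives

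*Combined protocol and SAP*

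**What the plan says.** **Analysis set.** Section 9.5.1: "All secondary efficacy analyses will be based on the mITT Analysis Set". Section 9.4.4 defines that set as "all randomized subjects who received at least one infusion of study drug", so serostatus plays no part.

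**Endpoint.** Among the between-arm comparisons of change from baseline to each visit, section 9.5.1 states that "laboratory parameters, such as autoantibodies (including antinuclear, anti-dsDNA, anti-Sm, and anti-RNP antibodies), complement factors (C3, C4), ESR, and CRP, will be summarized".

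**Stated interest.** Section 3.1: "Anti-Sm and anti-RNP autoantibodies will be assessed with particular interest, since their production may especially depend on TLR7".

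**Planned numbers.** Section 9.2: "The study will enroll up to 24 subjects with SLE in 2 parallel arms randomized to receive 2:1 DS-7011a or placebo", and "Also, tentatively, 9 of these 24 subjects will be positive for anti-Sm and/or anti-RNP autoantibodies".

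**Entry criteria.** Section 5.1 asks for antinuclear antibody ("including documented history of positivity for antinuclear antibody") but not for anti-Sm, anti-RNP or anti-dsDNA.

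**Assays.** Table 1.1 assigns the autoantibodies to "local laboratory at Screening and central laboratory thereafter". Section 8.6.8 gives samples at Screening, predose on Days 1, 29 and 57, and on Days 85 and 113. The note to Figure 1.1 labels Day 1 as baseline.

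The protocol describes no baseline-positive subset or serostatus subgroup. Sections 6.3.1 and 8.5 mention no stratification by serostatus.

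**The concern.** A subject without anti-Sm or anti-RNP at baseline has essentially no antibody to lose. That subject's change is assay noise around zero on either treatment. On the planned numbers such subjects are the majority (15 of 24), and they enter the same mean and median as the subjects in whom an effect could be seen. The protocol sets a recruitment target for positive subjects, but no analysis of these antibodies uses it.

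Section 9.2 infers initial efficacy from consistent impact across several endpoints, gives more weight to a large impact, and sets its extent against that reported for other antibodies to inform go/no-go. A summary that shrinks the apparent size of effect by construction weakens that reading for the autoantibodies that the protocol considers most informative about TLR7.

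**Working it through.** The plan gives no power, effect size or SD to reproduce. Its only figure on this point is the tentative 9 of 24.

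**Inputs from the documents**
- N = 24 at 2:1, so 24 × 2/3 = 16 on DS-7011a and 24 × 1/3 = 8 on placebo (section 9.2).
- 9 positive for anti-Sm and/or anti-RNP, tentative (section 9.2). Share p = 9/24 = 0.375 = 3/8.

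**Assumptions**
- Seronegative subjects change by about zero.
- Allocation is independent of serostatus.

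**1. Mean.** If positives on drug change by d more than positives on placebo, the expected all-mITT difference is p × d + (1 − p) × 0 = 0.375 d. With d = 50 units (an assumption), this is 18.75. With other numbers positive, the factor is 6/24 = 0.25 or 12/24 = 0.50. The 9 counts either antibody, so the factor for anti-Sm alone or anti-RNP alone is at most 3/8.

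**2. Median.** If 7 or fewer of the 16 DS-7011a subjects are positive, at least 9 are negative. The 8th and 9th ordered changes must then lie within the range of the seronegative values. The number positive on DS-7011a, X, is hypergeometric (24 subjects, 9 positive, 16 drawn):
- P(X = 9) = C(16,9)/C(24,9) = 11,440/1,307,504 = 0.0087
- P(X = 8) = 8 × C(16,8)/C(24,9) = 102,960/1,307,504 = 0.0787
- P(X ≤ 7) = 1 − 0.0087 − 0.0787 = 0.9125

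| Positives among 24 | Mean factor | P(7 or fewer of 16 on DS-7011a) |
|---|---|---|
| 9 | 0.375 | 0.91 |
| 10 | 0.417 | 0.77 |
| 12 | 0.500 | 0.33 |

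**3. Simulation under assumed values.** Positives change by −50 (SD 20) on drug and 0 (SD 20) on placebo; negatives change by 0 (SD 2). With 9 positives:
- The mean factor was 0.377. Its 2.5 to 97.5 percentile range was about 0.11 to 0.62, from noise and from chance imbalance in serostatus.
- The DS-7011a median was within 5 units of zero in 92% of runs.

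With 12 positives the typical median was about −12, so the median point largely fails there.

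**4. Does restricting to positives lose information?** Expected positives are 16 × 9/24 = 6 on drug and 8 × 9/24 = 3 on placebo. Using the values in step 3:
- Positives only: SE = √(400/6 + 400/3) = 14.14, and 50/14.14 = 3.5.
- All mITT, drug variance: 0.375 × 400 + 0.625 × 4 + 0.375 × 0.625 × 2,500 = 738.4.
- All mITT, placebo variance: 0.375 × 400 + 0.625 × 4 = 152.5.
- All mITT: SE = √(738.4/16 + 152.5/8) = 8.08, and 18.75/8.08 = 2.3.

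On these values the smaller subset shows the effect more clearly.

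**5. How thin single-antibody subsets could be.** The documents give no number for either antibody alone. If 5 of 24 carry it (an assumption), P(0 or 1 positive on placebo) = (4,368 + 14,560)/42,504 = 0.45. If 4 of 24 carry it, (1,820 + 4,480)/10,626 = 0.59.

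**The case against.** **Scale.** Section 9.5.1 says change from baseline, not percent change. A reader might infer that a true 50% fall would be reported as about 19%, or as little or no change. That holds only when individual percent changes are averaged with negatives counted as zero. On the absolute scale the baseline mean is diluted too. As an illustration with assumed values, let positives fall from 100 to 50 and negatives stay at 1. The expected arm baseline mean is (9 × 100 + 15 × 1)/24 = 38.1 and the mean change is −18.75, a 49% fall when the two are read together. This objection stands. The absolute mean change is still cut to about 3/8, but a reader who sets it against the baseline mean could recover much of the relative effect.

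**Median.** It is tempting to say that the median will be near zero. It is very likely at 9 positives and unlikely at 12, and the 9 is tentative. This also stands, and the claim must be conditional.

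**Unanswerable objective.** A reader might conclude that the trial cannot answer the autoantibody objective. The documents do not support that. Every subject is sampled repeatedly, so a baseline-positive summary can be produced from the planned data. Section 9.1 says that no hypothesis is tested, and section 9.2 relies mainly on CLASI-A. What is at risk is a visible signal in a descriptive reading, not formal power.

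**Deferral to the SAP.** Section 9.5 leaves the analysis populations to a SAP finalised before database lock, so a subset could still be added. That is true, and we cannot say that the final SAP lacks one. But section 9.5.1 already fixes mITT for these endpoints, and a subset first defined after unblinding would look post hoc.

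**Conclusion.** The concern holds in conditional form. As written, the mITT summary reports a mean absolute (or mean individual percent) change of about 3/8 of that in positive subjects, and at most 3/8 for anti-Sm or anti-RNP alone. With 9 positives there is a 91% chance that the DS-7011a median is near zero whatever the drug does. That chance is 77% at 10 positives and 33% at 12.

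These figures rest on three things: roughly zero change in seronegative subjects, allocation not stratified by serostatus, and a number positive close to the tentative 9 of 24. They apply to anti-Sm and anti-RNP. The documents give no expected number positive for anti-dsDNA.

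The consequence is a signal that may be masked in a descriptive go/no-go reading. It is worth correcting before database lock.

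**What to change.** In section 9.5.1 and the SAP, keep the all-mITT table as supportive and add the following beside it:

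- **Baseline-positive summary.** By arm, change in anti-Sm and in anti-RNP, as log ratio or percent change from Day 1, among mITT subjects positive for that antibody on the Day 1 predose central-laboratory sample. Use that sample rather than the local Screening result, so that status and change come from the central laboratory.
- **Individual profiles** over time for those subjects.
- **Negative-to-positive conversion**, reported separately in baseline-negative subjects.

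The same display can be used for anti-dsDNA.

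The cost is a short addition to the text, with no new samples or visits. The downside is small numbers: an expected 6 versus 3 for the two antibodies combined, and possibly fewer for each. A reader should not take 6 versus 3 as the count for each antibody. A placebo subset could be nearly empty, as step 5 of the working shows, so the display must stay descriptive and the individual profiles matter as much as the summary statistics.

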9.5.2. Safety Data Analyses

All safety analyses will be based on the Safety Analysis Set. All AEs will be coded using the Medical Dictionary for Regulatory Activities (MedDRA). Incidence summary of participants with TEAEs will be presented by maximum severity, SAEs, AESIs, AEs assessed as related to study drug, and AEs resulting in discontinuation of study drug. Observations at each visit and changes from baseline in vital sign recordings, results of laboratory analyses, ECG findings, Ig (IgM, IgG, IgA) values, vaccine (diphtheria, tetanus, and pneumococcus) titers, and lymphocyte subset (CD3-, CD4-, CD8-, CD20-, CD16-, CD56-positive) values will be numerically summarized by treatment group over time. Physical examination findings at each evaluation will be listed.

Listings of all safety endpoints will be generated.

Any medication (other than study drugs) taken by subjects during the course of the study will be recorded and coded using the World Health Organization (WHO) drug dictionary.

9.5.2.1. Treatment-Emergent Adverse Events

TEAEs are defined as new AEs that occur after the first dose of study drug or as AEs that were present prior to the dose of study drug but which worsened in severity after the start of study drug. An AE will be assigned to the study day in which it started, even if it resolved on a subsequent day. The incidence of TEAEs will be summarized by treatment group.

TEAEs will be further summarized by intensity (Section 10.4.4) and relationship to study drug (Section 10.4.5). Similarly, the number and percentage of subjects reporting treatment-emergent SAEs and related treatment-emergent SAEs will be tabulated, and TEAEs leading to discontinuation of study drug will be tabulated.

A by-subject AE (including treatment-emergent) data listing including but not limited to verbatim term, preferred term (PT), system organ class (SOC), intensity, and relationship to study drug will be provided. Deaths, SAEs, and AEs associated with study drug discontinuation will be listed.

AEs due to COVID-19 will be also summarized and listed.

9.5.2.2. Vital Signs

Descriptive statistics will be provided for vital signs measurements by scheduled time of evaluation and by treatment group, as well as for the change from baseline.

A listing of vital sign data will be generated.

9.5.2.3. Electrocardiograms

Descriptive statistics will be provided for the ECG measurements by scheduled time of evaluation and by treatment group, as well as for the change from baseline. In addition, the number and percentage of subjects with ECG interval values meeting the criteria will be tabulated (eg, QTc \leq 450 ms, >450 to \leq 480 ms, >480 ms to \leq 500 ms, and >500 ms) as well as any increase in QTc from baseline as follows: QTcF >60 ms above baseline in the 12-lead ECG, confirmed (persistent for >5 minutes) on repeated 12-lead ECGs.

A listing of ECG data will be generated.

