8.8.6. Electrocardiograms

Triplicate ECGs (approximately 1 minute apart) will be taken at Screening, on Day 85 and on Day 113 as shown in the SoE ([Table 1.1](#)). ECGs will be obtained after the subject has rested in a supine position for at least 5 minutes. When a blood collection is scheduled concomitantly with an ECG, the ECG should be taken at least 5 minutes prior to the blood collection.

Allowable time windows for ECGs are provided in Section [10.5](#).

At any visit during which a subject exhibits ECG abnormalities (eg, a heart rate ≤ 50 bpm) based on triplicate ECG readings, additional readings may be performed according to the investigator's discretion. ECG abnormalities that are considered clinically significant and that occur after the study drug administration will be reported as AEs. The following information will be recorded for any visit foreseeing ECG reading: Confirmation if ECG reading was indeed performed or not, date, and values of heart rate, PR interval, RR interval, QT interval, and QTcF interval.

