10.4.8. Adverse Event Outcome

- Recovered/Resolved
 - The subject fully recovered from the AE with no sequelae observed.
- Recovered/Resolved with Sequelae
 - The subject fully recovered from the AE but with sequelae.
- Recovering/Resolving
 - The AE is improving but not recovered.
- Not Recovered/Not Resolved
 - The AE continues without improving.
- Fatal
 - Fatal should be used when death is a direct outcome of the AE.
- Unknown

10.5. Appendix 5: Allowable Time Windows for Vital Signs, ECGs, and PK/PD Blood Draws

Table 10.2: Allowable Time Windows for Vital Signs, ECGs, and PK/PD Blood Draws

Vital Signs/ECG Procedures (in order of collection)	Allowable Time Window	
	Screening and Day 1	Day 1 and up to Follow-up Visit/End of Study Visit
Vital signs relative to drug administration should be taken:	No more than 5 minutes before the blood collection for safety measurements (inclusive of at least 5 minutes of supine rest with 5 additional minutes allowed).	Vital signs should be taken no more than 10 minutes before PK/PD blood draws (inclusive of at least 5 minutes of supine rest with 1 additional minute allowed). The time between the completion of vital signs and the blood draw may be expanded to 20 minutes when an ECG is scheduled to precede the PK/PD blood draw.
Triplicate 12-lead ECGs should be taken:	No more than 15 minutes before the blood collection for safety measurements (inclusive of at least 5 minutes of quiet rest in the supine position). Allow approximately 2 minutes between triplicate ECGs with 1 additional minute allowed between each of the triplicate ECGs.	When a PK/PD blood collection is scheduled concomitantly with an ECG, then ECG should be taken no more than 15 minutes before the PK/PD blood draws (inclusive of the at least 5 minutes of supine rest with 1 additional minute allowed).
PK/PD Procedures (in order of collection)		Allowable Time Window
PK/PD blood samples		
Days 1, 29, and 57: predose		15 minutes
Day 2 (24 hours after treatment administration)		±60 minutes
Day 8 (1 week after treatment administration)		±1 day
Days 1, 29, and 57: end of infusion		+5 minutes
Days 85, 113, and 169		±3 days
TLR7 and IFN-Type I drawn predose on Day 1 with PD blood sample, on Days 2, 8, 29, 57, 85, and 113		Not applicable

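### The tabulated count of QTcF rises above 60 ms depends on optional, untimed repeat ECGs and is therefore biased downwards

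*Combined protocol and SAP*

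**What the plan says.** Section 9.5.2.3 defines the one tabulation of large QTc increases as a QTcF more than 60 ms over the baseline value, "confirmed (persistent for >5 minutes) on repeated 12-lead ECGs". The same section also plans descriptive statistics for the ECG measurements and their change from baseline, a table of absolute QTc categories, and a listing. None of these carries a persistence condition.

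Section 8.8.6 sets the recordings: "Triplicate ECGs (approximately 1 minute apart) will be taken at Screening, on Day 85 and on Day 113". If an abnormality is seen on the triplicate, "additional readings may be performed according to the investigator's discretion"; the example given is a low heart rate. The items to be recorded at an ECG visit are "Confirmation if ECG reading was indeed performed or not, date, and values of heart rate, PR interval, RR interval, QT interval, and QTcF interval".

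Table 10.2 (Section 10.5) gives a different spacing: "Allow approximately 2 minutes between triplicate ECGs with 1 additional minute allowed between each of the triplicate ECGs". That entry stands in the column for Screening and Day 1. The column for later visits says that the "ECG should be taken no more than 15 minutes before the PK/PD blood draws" but gives no gap between the three readings.

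Table 1.1 agrees with Section 8.8.6 on the ECG visits: Screening, Day 85 and Day 113.

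**The concern.** The analysis rule asks for something that the scheduled recordings are not set up to deliver. A subject whose three readings on Day 85 are all more than 60 ms above baseline is not counted unless the site chooses to record again later and the interval can be shown to exceed 5 minutes. Nothing obliges the site to do either.

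ECG findings belong to the primary safety endpoint (Table 3.1), and the study is meant to inform a decision on further development (Section 2.2). A low or zero count in this row would be read as reassurance. Part of that reassurance could come from repeats not having been taken.

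Two loose ends affect the same row. Section 9.5.2.3 does not say which recording is the ECG baseline, and the two statements of triplicate spacing disagree.

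**Working it through.** The plan gives no expected QTcF count and no power calculation, so there is no figure of its own to reproduce. The check has three parts.

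**1. Time covered by a triplicate.** Three readings have two gaps, so the span from first to third is 2 × gap.

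| Source | Gap | Span | More than 5 min? |
|---|---|---|---|
| Section 8.8.6 (all ECG visits) | 1 min | 2 × 1 = 2 min | No |
| Table 10.2, Screening and Day 1 column, nominal | 2 min | 2 × 2 = 4 min | No |
| Same entry, full extra minute at both gaps | 2 + 1 = 3 min | 2 × 3 = 6 min | Yes |

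The gap would have to exceed 5/2 = 2.5 minutes. The criterion is applied on Days 85 and 113, where the only stated spacing is that of Section 8.8.6. The 4- and 6-minute spans belong to a column that does not cover those visits. From the scheduled post-dose triplicates alone, the confirmed count is therefore zero.

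**2. Loss when confirmation is optional.** Up to 24 subjects at 2:1 give 24 × 2/3 = 16 on active drug. Let p be the share with a sustained rise above 60 ms and q the chance that a qualifying later reading is taken and can be timed. Both are assumptions; the documents give neither. The expected confirmed count is 16 × p × q, and the chance of at least one is 1 − (1 − pq)^16. Each cell shows the expected count, with that chance in brackets.

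| p | q = 0 | q = 0.25 | q = 0.5 | q = 1 |
|---|---|---|---|---|
| 5% | 0 (0) | 0.2 (0.182) | 0.4 (0.333) | 0.8 (0.560) |
| 10% | 0 (0) | 0.4 (0.333) | 0.8 (0.560) | 1.6 (0.815) |
| 20% | 0 (0) | 0.8 (0.560) | 1.6 (0.815) | 3.2 (0.972) |

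The count still rises with the true rate whenever q is above zero, but it is scaled down by a factor that nobody will know.

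**3. Whether the other outputs would pick up the case.** Suppose a baseline of 380 ms and a rise of 65 ms: 380 + 65 = 445 ms.

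- Absolute categories: 445 ms is in the lowest one (up to 450 ms), so nothing shows.
- Arm mean change: if the other 15 active subjects did not change, the mean moves by 65/16, about 4 ms.
- Listing: the case is there, as it is in the data behind the change-from-baseline summaries. A reported maximum change would show it.

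**Baseline.** Table 1.1 and Section 8.8.6 schedule no pre-dose ECG other than Screening, which may be up to 28 days before randomization. The note to Figure 1.1 labels Day 1 as baseline, but no ECG is scheduled that day. The ECG baseline is thus in effect the Screening recording, and Section 9.5.2.3 does not say so.

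**The case against.** The best defence is that the rule never asked the triplicate to prove persistence. Confirmation on repeated ECGs reads naturally as recordings taken after an abnormal finding, and Section 8.8.6 allows these; its heart-rate example is only an example. That stands: the criterion can be met. A reader might infer that the count goes to zero whatever the drug does. The documents do not support that, because it would require that no site ever re-records.

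A reader might also infer that a QTcF effect would go unseen. That is not supported either. The category table, the change-from-baseline summaries and the listing are free of the condition, and Section 8.8.6 has clinically significant post-dose ECG abnormalities reported as adverse events. One descriptive row is affected, in a study that tests no hypothesis (Section 9.1). Sites are blinded, so there is no reason to expect re-reading to differ by arm; cases would be lost in both.

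Three further replies carry some weight. Persistence guards against transient readings, which is a fair aim. Section 9.5 foresees a SAP, finalized before database lock, that may define the derivation. The case report form may capture times even though Section 8.8.6 does not list them.

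What remains is that, on the text available, confirmation is optional and has neither a QTcF trigger nor an interval, and the listed data could not show that 5 minutes had passed. A rise that is measured against Screening, and that leaves the absolute value within the lowest category, may give the investigator no cue to repeat.

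**Conclusion.** The concern holds in a limited form. The row for QTcF rises above 60 ms relies on optional, untimed repeat recordings, so it undercounts by an unknown factor, and it is zero if only the scheduled post-dose triplicates are available. A zero in that row could mean no effect or no repeats, and the table alone would not tell which.

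Severity is minor to moderate: the affected row is part of the primary safety endpoint, but the underlying values are collected, summarized and listed without the condition. The conclusion assumes the 1-minute spacing of Section 8.8.6 on Days 85 and 113 and no further derivation rule elsewhere. The counts in the working are illustrations, since p and q are assumed.

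**What to change.** In Section 9.5.2.3 and the SAP:

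- Tabulate by arm the number and percentage of subjects whose triplicate-mean QTcF is more than 60 ms above the baseline triplicate mean, with no persistence condition.
- Report any confirmed count (more than 5 minutes) beside it as a secondary row. For that row to be derivable, the clock time of each reading must be recorded.
- State that the ECG baseline is the Screening triplicate mean.
- Reconcile the triplicate spacing between Section 8.8.6 and Table 10.2.

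The main row uses data already planned and needs no extra ECG. The cost is one table row and a correction of wording. The main count may be higher and less favourable, and may include transient rises; the secondary row keeps the sponsor's guard against those.
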